3.1.1.2 Systemic events

Symptoms of systemic events assessed by trial subjects and recorded in the e-diary are fever, fatigue, headache, chills, vomiting, nausea, diarrhea, new or worsened muscle pain, and new or worsening joint pain from Day 1 through Day 7 inclusive, where Day 1 is the day of each IMP injection. The derivations for systemic events will be handled similar to the way local reactions are handled for presence of an event, severity level, duration, and onset day.

Fever is defined as an oral temperature $\geq 38.0^{\circ}\text{C}$ (100.4°F). Temperatures collected in degrees Fahrenheit will be converted to degrees Celsius using $(^{\circ}\text{F} - 32) \times 5/9$ and grading will be based on the unrounded conversions. An investigator or medically qualified person

must confirm a trial subject's fever as $>40.0^{\circ}\text{C}/>104.0^{\circ}\text{F}$ before it is entered in the trial database.

The highest oral temperature for each day will be recorded in the e-diary and the maximum temperature from Day 1 through Day 7 will be graded as described in [Table 6](#).

Solicited systemic events will be categorized as mild, moderate, severe, or potentially life-threatening) and graded from 1 to 4, during the analysis as described in [Table 6](#).

Table 6. Systemic events grading scale

	Mild (Grade 1)	Moderate (Grade 2)	Severe (Grade 3)	Potentially life-threatening (Grade 4)
Fever (oral temperature of $\geq 38.0^{\circ}\text{C}/\geq 100.4^{\circ}\text{F}$)	$\geq 38.0^{\circ}\text{C}/\geq 100.4^{\circ}\text{F}$ to $38.4^{\circ}\text{C}/101.1^{\circ}\text{F}$	$\geq 38.5^{\circ}\text{C}/\geq 101.2^{\circ}\text{F}$ to $38.9^{\circ}\text{C}/102.0^{\circ}\text{F}$	$\geq 39.0^{\circ}\text{C}/\geq 102.1^{\circ}\text{F}$ to $40.0^{\circ}\text{C}/104.0^{\circ}\text{F}$	$>40.0^{\circ}\text{C}/>104.0^{\circ}\text{F}$
Vomiting	1 to 2 times in 24 h	>2 times in 24 h	Requires intravenous hydration	Emergency room visit or hospitalization for hypotensive shock
Diarrhea	2 to 3 loose stools in 24 h	4 to 5 loose stools in 24 h	6 or more loose stools in 24 h	Emergency room visit or hospitalization for severe diarrhea
Headache	Does not interfere with activity	Some interference with activity	Prevents daily routine activity	Emergency room visit or hospitalization for severe headache
Fatigue/tiredness	Does not interfere with activity	Some interference with activity	Prevents daily routine activity	Emergency room visit or hospitalization for severe fatigue
Chills	Does not interfere with activity	Some interference with activity	Prevents daily routine activity	Emergency room visit or hospitalization for severe chills
Nausea	No interference with activity or 1 to 2 episodes/24 h	No interference with activity or >2 episodes/24 h	Prevents daily activity, requires outpatient intravenous hydration	Emergency room visit or hospitalization for hypotensive shock
New or worsened muscle pain	Does not interfere with activity	Some interference with activity	Prevents daily routine activity	Emergency room visit or hospitalization for severe new or worsened muscle pain

	Mild (Grade 1)	Moderate (Grade 2)	Severe (Grade 3)	Potentially life- threatening (Grade 4)
New or worsening joint pain	Does not interfere with activity	Some interference with activity	Prevents daily routine activity	Emergency room visit or hospitalization for severe new or worsened joint pain

3.1.1.3 Adverse events and serious adverse events

For all dosed trial subjects in cohorts 1-8, AEs will be collected from each dose up to 1 month after this dose and for subjects in cohort 9 - from the Visit 1 (after eligibility is confirmed) up to 1 month. However, for any visit more than 1 month after each IMP injection (cohorts 1-8) or Visit 1 (cohort 9), only IMP-related AEs, trial procedure-related AEs, adverse events of special interest (AESIs), SAEs, and AEs linked to confirmed COVID-19 cases will be recorded.

Solicited AEs (i.e., reactogenicity events) that are derived from trial subjects' e-diaries should not be reported as AEs unless the event meets criteria for an SAE or starts after Day 7 or starts on Days 1 to 7 and continues past Day 7.

In addition, all solicited Grade 4 reactogenicity events should be medically confirmed.

An AE/SAE is defined as treatment-emergent adverse event (TEAE) if the event onset date and time is after the first IMP dose (if the event was absent before the first administration of the IMP) or worsened after the first IMP dose (if the event was present before the first administration of the IMP).

In the event of an incomplete onset date, the event will be considered as treatment-emergent unless the partial onset date information or complete or partial end date confirms the onset date or the event end prior to the first dose of IMP.

Missing AE date will be addressed as described in [Section 5.3](#).

All AEs and SAEs will be coded/categorized according to terms in Medical Dictionary for Regulatory Activities (MedDRA®) version 26.0 or higher.

3.1.2 Immunogenicity endpoints – Part B

For both BNT162b2-experienced subjects and COVID-19 vaccine-naïve subjects the primary immunogenicity endpoints are:

- Reference and variant of concern (VOC) specific neutralizing titers (NTs)
- Reference and VOC specific seroresponse (SRs)

The primary immunogenicity endpoints, for subjects assigned to Part B, are evaluated against the reference at the following time points:

- VOC (B.1.1.7 and B.1.617.2) specific NTs 1 month after one dose of BNT162b2 (B.1.1.7 + B1.617.2) for subjects in Part B Cohort 1 vs reference strain NTs 1 month after two doses of BNT162b2 for subjects from the Phase III trial BNT162-02 / C4591001
- VOC (B.1.617.2) specific NTs 1 month after one dose of BNT162b2 (B1.617.2) for subjects in Part B Cohort 4 vs reference strain NTs 1 month after two doses of BNT162b2 for subjects from the Phase III trial BNT162-02 / C4591001
- Reference strain NTs 3 weeks after one dose of BNT162b2 (B.1.1.7 + B1.617.2) for subjects in Part B Cohort 6 with evidence of prior infection vs reference strain NTs 1 month after two doses of BNT162b2 for subjects without evidence of infection from the Phase III trial BNT162-02 / C4591001
- VOC (B.1.1.7 and B.1.617.2) specific NTs 1 month after two doses of BNT162b2 (B.1.1.7 + B1.617.2) for subjects in Part B Cohort 6 vs reference strain NTs 1 month after two doses of BNT162b2 for subjects from the Phase III trial BNT162-02 / C4591001. The non-inferiority test for this primary immunogenicity comparison will not be performed. The details of clinical and statistical considerations are described in [Section 8.2](#).

Titers above the lower limit of quantitation (LLOQ) are considered accurate and their quantitated values will be presented. Values below the LLOQ will be set to 0.5× LLOQ for analysis and values above ULOQ will be set to ULOQ.

SR is defined as a ≥4-fold rise in neutralizing titer from baseline. For subjects with a baseline titer less than the lower limit of quantitation (<LLOQ), seroresponse is defined as a post-vaccination titer of ≥4 × LLOQ.

3.1.3 Immunogenicity endpoints – Part C

For subjects randomized to Part C Cohorts 7 and 8, the primary immunogenicity endpoints are:

- VOC (Omicron BA.1) specific NTs
- VOC (Omicron BA.1) specific SRs

The primary immunogenicity endpoints for subjects randomized in Part C Cohort 7 and 8 are evaluated 1 month after one dose of BNT162b2(B1.1.529) in Cohort 7 and compared to those at 1 month after one dose of BNT162b2 in Cohort 8.

3.2 Secondary endpoints

3.2.1 Immunogenicity endpoints

Part A

After one, two, or three doses of BNT162b2 (B.1.1.7 + B.1.617.2), BNT162b2 (B.1.1.7), BNT162b2 (B.1.617.2), and BNT162b2 the secondary immunogenicity endpoint is:

- Reference and VOC (B.1.1.7 and/ or B.1.617.2) specific NTs at each post-vaccination time point

Part B

For both BNT162b2-experienced subjects and COVID-19 vaccine-naïve subjects the secondary immunogenicity endpoint is:

- Reference and VOC specific NTs (B.1.1.7 and B.1.617.2) at 1 month after one dose of BNT162b2 (B.1.1.7 + B.1.617.2) or BNT162b2 (B.1.617.2) in BNT162b2-experienced subjects vs 1 month after two doses of BNT162b2 for subjects from the Phase III trial BNT162-02 / C4591001
- Reference and VOC specific NTs (B.1.1.7 and B.1.617.2) at 1 month after two doses or three doses of BNT162b2 (B.1.1.7 + B.1.617.2) in COVID-19 vaccine-naïve subjects
- VOC specific NTs (B.1.1.7, B.1.617.2, and B.1.1.529.5) at 3 weeks after one dose of BNT162b2 (B.1.1.7 + B.1.617.2) in COVID-19 vaccine-naïve subjects with evidence of prior infection vs 1 month after one booster dose of BNT162b2 (B.1.1.7 + B.1.617.2) in BNT162b2-experienced subjects without evidence of infection
- VOC specific NTs (B.1.1.7, B.1.617.2, B.1.1.529.5) at 3 weeks after one dose of BNT162b2 (B.1.1.7 + B.1.617.2) in COVID-19 vaccine-naïve subjects with evidence of prior infection vs 1 month after two doses of BNT162b2 (B.1.1.7 + B.1.617.2) in COVID-19 vaccine-naïve subjects without evidence of infection

Part C

For all Cohorts in Part C of the trial, the secondary immunogenicity endpoint is:

- VOC (Omicron BA.1) specific NTs at each post-vaccination time point

3.3 Exploratory endpoints

Part A

Below are exploratory endpoints for Part A:

- Reference and VOC specific NTs (B.1.1.7 and/ or B.1.617.2) at each post-vaccination time point. This endpoint is duplicate of the secondary endpoint and the analysis will not be performed.
- CD4+ and CD8+ T-cell responses (Ex vivo ELISpot)

Part B

Below are exploratory endpoints for Part B:

- Reference and VOC (B.1.1.7 and/ or B.1.617.2) specific NTs at each post-vaccination time point
- Nucleocapsid (N)-binding antibody seroconversion in subjects with no serological or virological evidence of past SARS-CoV-2 infection or confirmed COVID-19
- Number of confirmed COVID-19 cases

Part C

Below are exploratory endpoints for Part C:

- Reference and VOC (Omicron BA.1) specific NTs at each post-vaccination time point
- Number of confirmed COVID-19 cases

The exploratory analyses not specified in this section are out of scope of this SAP and may be described in a different document.

3.3.1 Confirmed COVID-19 cases

Confirmed COVID-19 case is defined in BNT162-17 protocol v7 Section 8.2.4:

- Presence of SARS-CoV-2 NAAT-positive at a local testing facility (using an acceptable test) and COVID-19 reported AE (symptomatic).

OR

- presence of at least 1 of the symptoms as listed in the BNT162-17 protocol v7 Section 8.2.4 and
- SARS-CoV-2 NAAT-positive at the central laboratory during, 4 days before or after the symptomatic period.

The surveillance period will start post first dose of vaccination until the earliest of the following events:

- Onset date of the first confirmed COVID-19 case reported as AE.

OR

- First symptom or positive central NAAT date (whatever is earlier) identified via the above algorithm.
- When the subject's end of trial occurs due to withdrawal of consent, lost to follow-up, death, investigator/sponsor/subject decision, clinical trial completion, adverse event, protocol deviation or other.

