Day (relative to Visit 1 on Day 1)	-7 to -1	1	8+2	29±3	180±10	360±10		
Oral swabs for SARS-CoV-2 sequencing d	X	X	X	X	X	X	X	X
Blood draws for serological testing for SARS-CoV-2 N-binding antibodies and for humoral immunogenicity assessments (20 mL) f		X	X	X	X	X	X	X i
Record pregnancies		Start	=>	=>	=>	End	End	

Notes: The SoA allows for *ad hoc* visits for SARS-CoV-2 testing for symptomatic or asymptomatic subjects. "BNT162b2-experienced" is defined as subjects who have previously received two injections of 30 µg BNT162b2.

- a At Visit 0: complete physical examination including body weight, vital signs (oral body temperature, heart rate, blood pressure [systolic and diastolic]), blood and urine clinical laboratory tests; at Visit 1: symptom-orientated physical examination.
- b If the result from an oral swab for NAAT-based SARS-CoV-2 is not older than 24 h at the planned time of IMP injection, availability of the test result from Visit 1 on Day 1 is optional.
- c Issue thermometer or other measuring device for subjects to measure their oral body temperature each day and if they experience flu-like symptoms.
- d All swabs will be analyzed, even if no COVID-19 symptoms are shown.
- e For any visits >1 month after each IMP injection, only IMP-related AEs, trial procedure-related AEs, AESIs, any SAEs. In addition, all AEs linked to confirmed COVID-19 cases will be recorded.
- f Serum samples will be stored and may be analyzed retrospectively for additional clinical parameters (troponin, cytokine).
- g The 12-lead ECG at Visit 1 can be skipped if the 12-lead ECG from Visit 0 was performed within 24 h prior to the planned IMP dose.
- h The recording will start from IMP allocation during Visit 1 (after eligibility is confirmed and the subject is withdrawn from the trial BNT162-02 / C4591001 [NCT04368728]).
- i Subjects who receive non-trial SARS-CoV-2 vaccinations will be discontinued, resulting in an early termination visit. For subjects who receive non-trial SARS-CoV-2 vaccinations, there will be no blood sampling for humoral immunogenicity or T-cell and B-cell response assessments at the early termination visit.
- j If an *ad hoc* visit occurs in combination with a planned visit, blood sampling will only be one 20 mL sample for serological testing for SARS-CoV-2 N-binding antibodies and humoral immunogenicity assessments.
- k For any visits >1 month after each IMP injection, only prohibited medications should be recorded.

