### **8.3.1 Time period and frequency for collection of AE, AESI, and SAE information**

All AEs, AESI, and SAEs (including a death) will be recorded at the time points listed in the SoA in Section 1.3.

For subjects who receive a non-trial SARS-CoV-2 vaccination, AEs/SAEs will be collected as specified above until the date when the subject was vaccinated with the non-trial SARS-CoV-2 vaccine. The AEs/SAEs expected to be captured after non-trial SARS-CoV-2 vaccination are within the frame of post-marketing safety data reporting.

Cohort 9 subjects will be offered a booster vaccination with the locally marketed Pfizer-BioNTech RNA-based COVID-19 vaccine after the EOT has been completed. If subjects choose to receive this vaccination, the recording and follow-up of any safety events will

follow post-marketing rules and such events will not be recorded within the trial documentation.

Investigators are not obligated to actively seek AEs or SAEs at any time after a trial subject has been discharged from the trial, however, if the investigator learns of any SAE (including a death), that they consider to be reasonably related to the IMP administration or trial participation, the investigator must promptly notify the sponsor.

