3.3.2 Nucleocapsid-binding antibody seroconversion

Nucleocapsid (N)-binding antibody seroconversion is defined as a positive N-binding antibody result after the first dose in subjects without serological evidence of previous infection (determined by negative N-binding antibody) at Visit 1 and without previous virological evidence of infection (determined by negative NAAT results at Screening and Visit 1).

The surveillance period will start after the first dose for subjects in Cohort 1, Cohort 4, and Cohort 6 in Part B until the earliest of the following events:

- Date of the first positive N-binding antibody test.
- or when the subject's end of trial occurs.

3.3.3 **CD4+ and CD8+ T-cell responses (Ex vivo ELISpot)**

T cell-mediated immune responses after one, two, or three doses of the multivalent vaccine BNT162b2 (B.1.1.7 + B.1.617.2), or one booster dose of the monovalent vaccine BNT162b2 (B.1.1.7), or one booster dose of BNT162b2 (B.1.617.2), at 30 µg will be analyzed. Cell-mediated immune (CMI) responses will be measured by interferon γ (IFNγ) enzyme-linked immuno spot (ELISpot).

T-cell responses of the trial subjects will be analyzed for both CD4+ and CD8+ T-cells specific for the SARS-CoV-2 reference strain full length spike (FL-S), SARS-CoV-2 FLS B.1.1.7 (“Alpha variant”), and SARS-CoV-2 FLS B.1.617.2 (“Delta variant”). The SARS-CoV-2 S protein will be tested using two peptide pools (Spike protein pool 1 [SP1]: N-terminal half; Spike protein pool 2 [SP2]: C-terminal half) for each variant. Hereinafter, “target” refers to the applied experimental stimulus (spike protein pool 1, spike protein pool 2, or the sum of spike protein pools 1 + 2) in the ELISpot readout.

For analysis of responders, the spot counts of the ELISpot assay will be evaluated with the ELISpot data analysis (EDA) tool. In the next steps, these results are checked by subject matter experts, and a final call on presence or absence of T-cell responses is made for each analyzed sample, hereinafter named “expert call”.

3.4 **Baseline and other variables**

3.4.1 **Definition of baseline value and SARS-CoV-2 infection at baseline and post vaccination**

Unless otherwise specified, the last non-missing measurement or sample collected prior to first IMP injection is considered the baseline data for all assessments.

Baseline in immunogenicity analysis:

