5.2 General methods

All statistical procedures will be completed using SAS version 9.4 or higher. Unless otherwise specified, 2-sided 95% CIs for all endpoints in the statistical analysis, will be presented. Data assessed after the vaccination with a non-trial COVID-19 vaccine will be excluded from all immunogenicity analyses.

Analysis of antibody titers will be performed on natural log scale and the results will be exponentiated back to original scale.

For each subject and each time point two titers for each variant will be determined, as each sample will be measured in replicate. The response per subject, variant, and time point is defined as the geometric mean of the two titers.

All relevant subject data, including those derived will be presented in individual subject data listings.

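### The COVID-19 and N-seroconversion rates do not stop person-time at a non-trial COVID-19 vaccination, and the N clock also runs past the last N test

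*SAP*

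**What the plan says.** **End of surveillance.** In SAP 3.3.1 the COVID-19 period runs from the first dose to the earlier of the case and the point when the subject's "end of trial occurs due to withdrawal of consent, lost to follow-up, death, investigator/sponsor/subject decision, clinical trial completion". The list of end-of-trial reasons closes with "clinical trial completion, adverse event, protocol deviation or other". In SAP 3.3.2 the N-seroconversion period ends at "Date of the first positive N-binding antibody test" "or when the subject's end of trial occurs". Receipt of a non-trial vaccine is in neither list. SAP 5.2.2 divides events by total person-years of follow-up.

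**After a non-trial vaccine.** The footnotes to the Protocol 1.3 schedules state: "Subjects who receive non-trial SARS-CoV-2 vaccinations will be discontinued, resulting in an early termination visit". Protocol 7.2 lists such a vaccination among the reasons for discontinuation from the trial. Protocol 8.3.1 says "AEs/SAEs will be collected as specified above until the date when the subject was vaccinated with the non-trial SARS-CoV-2 vaccine". For the early termination visit the footnotes add that "there will be no blood sampling for humoral immunogenicity or T-cell and B-cell response assessments at the early termination visit". In Protocol Table 4 a single 20 mL draw supplies both the N-binding serology and the humoral assessments. Surveillance swabs stay scheduled at that visit.

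**Data after the switch.** SAP 5.2 says "Data assessed after the vaccination with a non-trial COVID-19 vaccine will be excluded from all immunogenicity analyses". It has no matching rule for the two incidence rates.

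**The concern.** A rate per person-year needs its numerator and denominator to cover the same time at risk. Here they can part in two ways.

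- **COVID-19.** One of the two case routes in SAP 3.3.1 needs a COVID-19 AE. That route closes on the day of the non-trial vaccine, while person-time runs on to the recorded end of trial. A case found in between, for instance from a swab at early termination, would be credited to the trial vaccine although the subject had since received another.
- **N-seroconversion.** Status is unknown after the last N sample, yet the denominator runs to end of trial. This affects anyone who leaves without a final sample, including subjects lost to follow-up.

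Incidence per 1,000 person-years is the stated estimand for both endpoints in Part B and for COVID-19 in Part C. At stake is the accuracy of those descriptive rates.

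**Working it through.** The documents give no expected incidence, case count or person-time for these endpoints, so there is no planned figure to reproduce. The check asks how much unobserved time the stated rule can add.

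**Inputs from the documents.** Single-dose Part B cohorts (1 and 4), Protocol Table 4: Day 1, then visits at Days 8, 29, 180 and 360, each with an N draw.

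**Assumptions, not in the documents.**
- The share p of subjects who receive a non-trial vaccine is 5–30%.
- Switching is uniform over follow-up, with mean Day 180.5.
- The hazard is constant, and person-time removed by events is ignored.
- As the worst case, no event is recorded in the gap.
- The delay from switch to recorded end of trial is 0, 7 or 30 days, or lasts until the next scheduled visit.

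**Step 1: mean gap between a switch and the neighbouring visit.** The visit intervals are 7, 21, 151 and 180 days. The mean wait to the next visit is (7² + 21² + 151² + 180²) / (2 × 359) = 55,691 / 718 = 77.6 days, and the longest is about 180. By symmetry, the mean time since the previous visit is also 77.6 days.

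**Step 2: mean time per subject up to the switch or Day 360.** V = (1 − p) × 360 + p × 180.5. This gives 351.0, 342.1, 324.1 and 306.2 days for p = 5, 10, 20 and 30%.

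**Step 3: COVID-19 rate.** With a mean delay of g days, the counted time is V + p·g and the understatement is p·g / (V + p·g). Example for p = 30% at the next visit: 0.30 × 77.6 = 23.3, and 23.3 / (306.2 + 23.3) = 7.1%.

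| Delay | p = 5% | 10% | 20% | 30% |
|---|---|---|---|---|
| 0 days | 0 | 0 | 0 | 0 |
| 7 days | 0.1% | 0.2% | 0.4% | 0.7% |
| 30 days | 0.4% | 0.9% | 1.8% | 2.9% |
| Next visit | 1.1% | 2.2% | 4.6% | 7.1% |

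The same calculation for the three-dose Part B cohort gives a mean gap of 63 days and 0.8–5.5% in the last row.

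**Step 4: N-seroconversion rate with immediate discontinuation and no N sample at early termination.** The counted time is V, but the last 77.6 days of each switcher are unobserved. The understatement is p × 77.6 / V:

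- 5%: 3.9 / 351.0 = 1.1%
- 10%: 7.8 / 342.1 = 2.3%
- 20%: 15.5 / 324.1 = 4.8%
- 30%: 23.3 / 306.2 = 7.6%

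If discontinuation also waits for the next visit, the unobserved time doubles and the range becomes 2 × 3.9 / (351.0 + 3.9) = 2.2% to 2 × 23.3 / (306.2 + 23.3) = 14.1%.

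**The case against.** The strongest reply is that the switch is itself an end-of-trial event. The schedules require discontinuation, Protocol 7.2 lists it as a reason, and the last items in the SAP 3.3.1 list cover it. **This stands, and it limits the point.** A reader might infer from the missing censoring date that switchers keep adding person-time to Day 360, which would understate the rates by about 2.5–15% for 5–30% switching. The protocol rules that out. Only the interval to the recorded end of trial is open. If that date is set to the vaccination date, as Protocol 8.3.1 does for AE collection, the COVID-19 excess is zero. The documents do not say how it is dated, and the schedules give no time limit for the early termination visit.

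A reader might also infer that all sampling has stopped. That is not supported either. The footnote bars humoral and cellular blood but does not name N serology, surveillance swabs remain scheduled, and the symptom-plus-central-NAAT route is not expressly closed. What stands is an ambiguity: the barred humoral sample and the N sample are the same draw.

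Finally, these endpoints are exploratory, are presented by cohort and carry no test, and time to end of trial is a literal reading of person-years of follow-up. That lowers the priority. It does not make unobserved time informative about the rate. Ending N time at the last test is a choice of convention, but it is the one that matches what can be observed.

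**Conclusion.** The point holds in a limited form. The stated rules allow person-time with reduced ascertainment, and under another vaccine, into both rates, and the post-switch exclusion in SAP 5.2 is not extended to them. That both rates are in fact diluted is not shown; the size depends on a switching share and a delay that the documents do not give.

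- **COVID-19:** understated by 0 to about 3% if discontinuation follows within 30 days, and by about 1–7% if the switch is found only at the next scheduled visit, for 5–30% switching and no case recorded in the gap.
- **N-seroconversion:** about 1–8% under the same shares even with immediate discontinuation, provided no N blood is drawn at early termination. Subjects who leave for other reasons without a final sample add to this.

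The effect is small and confined to exploratory, descriptive rates. No hypothesis test or primary conclusion is affected.

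**What to change.** - In SAP 3.3.1 and 3.3.2, add the date of the first non-trial COVID-19 vaccination to the events of which the earliest ends surveillance, and do not count cases or seroconversions after it.
- In SAP 3.3.2, for subjects who have not seroconverted, end person-time at the last valid N-binding test on or before that date.
- State whether N-binding serology is drawn at the early termination visit after a non-trial vaccination, so that the schedule footnote and the shared draw can be reconciled.

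The cost is one derivation rule and slightly fewer person-years. The vaccination date should already be in the data, since Protocol 6.5.3 has prohibited medications recorded throughout participation.
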